## 15.7 Inclusion in the analysis

The primary analysis of this endpoint will be based on an intention to treat population, which includes all participants in the group to which they were randomised. A secondary analysis will be performed in a per-protocol population which will be defined prior to Trial Management System Database lock.

## 15.8 Health economic analysis

The economic evaluation will be conducted from the health care perspective in the first instance. To assess resource use in primary care, outpatient settings, hospitalisations, and prescribed regular and occasional-use medications, participants and GPs will be sent annual postal questionnaires. Medication use will also be collected at baseline. Unit costs will be applied to the reported resource use volumes, using unit costs obtained from standard national sources including Department of Health Reference Costs, the British National Formulary and Personal Social Services Research Unit (PPSRU) Costs.

Effectiveness will be measured by 1) the primary endpoint of cardiovascular mortality or morbidity, non-fatal myocardial infarction or stroke; and 2) quality adjusted life years. These will be measured and reported over the 5 years of the follow-up period and extrapolated in a long-term (lifetime) analysis. Incremental cost-effectiveness will be reported for each measure of effectiveness and for each time horizon.

Mean costs and effects, mean differences between the study groups, and incremental cost-effectiveness ratios and net benefit statistics will be reported. Parametric and non-parametric measures of uncertainty around each of these will be reported as appropriate. Results will be also presented in the form of cost-effectiveness planes and cost-effectiveness acceptability curves showing the probabilities that treatment with metformin is cost-effective compared with placebo at a range of willingness to pay thresholds. Sensitivity analyses will be undertaken to explore the effect on the results of different discount rates, future drug prices, and factors that may affect the generalisability of the study results.

The precise form of the extrapolation model will be explored during the feasibility phase and the early phases of the full study if it proceeds. Several well-validated models are available for cardiovascular disease and for diagnosed T2DM, including the UKPDS Outcomes Model 39 but not for people with non-diabetic hyperglycaemia, and model estimation and development will be required to link the GLINT population into existing disease models, and into existing screening models to inform decisions about population-based screening for CVD risk and individuals at high risk of developing T2DM.

# 15.9 Definition of the end of the study

The end of the full study will be the date when the final participant and GP questionnaires have been received for data entry. The date of the last point of contact will be the date of censor for participants who do not return a questionnaire.

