## 9.6 Changes in participant study status

Optimally, all participants should remain on study treatment and follow up for the duration of the study. However, it is recognized that in rare instances a participant may temporarily or permanently discontinue study medication or participation in the study.

Discontinuations from the study occur only if the participant explicitly withdraws consent for all forms of follow up.

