# 9.6.1 Discontinuation of study medication

Discontinuations from study treatment may occur for protocol-specified reasons (see below), due to the judgment of the primary investigator, or due to the participant's decision.

Protocol specified reasons for study drug discontinuation are:

• An adverse event which requires discontinuation of the study medication or results in inability to continue to comply with study procedures. Study drug can be resumed if the event resolves.

• Participant refuses follow up via participant annual questionnaire

• Development of chronic kidney disease (CKD stage 3b or worse, eGFR<45ml/min).

•Participant is temporarily not contactable

Participants are considered temporarily not contactable in the following situations:

- •Telephone contacts are made at 4 and 8 weeks. Sites will make three attempts to call the participant during this period. After three failed call attempts the participant is lost to follow up and the drug supply is stopped.
- •The participants are asked to complete and send a questionnaire at 4 months, then annually. Failure to return the questionnaire will result in a repeat issue of the questionnaire at 4 weeks after the due date and also at 8 weeks if required. Continued failure to return the questionnaire within another month results in an attempt to call the participant. After three failed call attempts the patient is lost to follow up and the drug supply is stopped.

For participants who fulfil the above criteria, attempts will be made annually to reestablish contact. If contact is re-established and the participant agrees, the drug will be re-started.

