# GP/participant questionnaire Mail Out (Issued after 4 months, annually and at end of study)

Participant questionnaire

- Self reported morbidity (CVD, cancer, T2DM)
- Medication adherence
- Health service use in past 12 months
- EuroQoL EQ-5D
- Treatment satisfaction/SF-8
- Self-Adverse events

GP questionnaire

- Vital status i.e. alive or dead
- Morbidity (CVD, cancer, T2DM)
- Current prescribed medication
- Adverse events
- Whether participant has become pregnant

Participants and GPs will be instructed to return the completed questionnaires to the DTU in freepost envelopes. If necessary, reminders will be sent after 4 and 8 weeks for the annual questionnaire. Participants will be contacted by phone if they do not respond to the reminders. Annual questionnaires will not be sent within 4 weeks of the end of study questionnaires being issued.

Participants and GPs will be reminded about the potential risks of taking metformin when they receive their four month questionnaire in the feasibility phase and the annual questionnaire in the full study.

When a participant or GP indicates that a primary or secondary endpoint has occurred following receipt of the annual questionnaire, information on this event will be collected immediately. We will also use information from the Office for National Statistics, the Cancer Registry and Health Episode Statistics to assess whether participants have experienced a study endpoint.

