#### 11.3.2 Additional Information

•B12 levels, LFTs, total cholesterol, LDL and HDL cholesterol will be collected at baseline and 6 months. B12 and LFT results will be reviewed following the feasibility phase to inform a decision on whether it is necessary to include these measures in the full study.

•HbA1c and serum creatinine will be collected at baseline, 3 months, and 6 months. Baseline HbA1c and serum creatinine should be used for assessment of eligibility. Creatinine results will be reviewed following the feasibility phase to inform a decision whether it is necessary to centrally monitor renal function in the full study.

•Feedback about study participation, including how to optimise medication adherence, will be sought through the invitation of a subset of volunteers to participate in focus groups.

•We will use information received from the Office for National Statistics, the National Cancer Registry and Health Episode Statistics to assess clinical primary and secondary outcomes. Any events found will be added manually to the GLINT Trial Management System Database.

All participants in the feasibility phase of the study will continue into the full study and receive scheduled assessments as described in Appendix 1.

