#### 13 Evaluation of Results (Definitions and response/evaluation of endpoints)

Study endpoints will be defined based on clinical standards, regulatory precedent, and historical trials. These definitions will be provided in an endpoint ascertainment manual for the Clinical Events Classification Committee (CEC). Participants and their GPs will be surveyed annually regarding procedures and hospitalisations which have taken place between study contacts. We may also conduct electronic READ code searches in participant GP records to search for relevant clinical outcomes. Medical records pertaining to hospitalisations and procedures of interest will be obtained and thoroughly reviewed in order to determine whether an event of significance has occurred. HES data will also be accessed to provide evidence for potential endpoints. This information will be collated and anonymised in an 'endpoint pack' and sent to the CEC for review.

Events included in the primary composite outcome, all-cause mortality, hospitalisations for heart failure and unstable angina, and coronary, cerebrovascular or peripheral revascularisations will be adjudicated by the CEC blinded to study treatment.

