#### 15.5 Procedure to account for missing or spurious data

In the analysis of the efficacy endpoints of the full study, participants who are lost to follow-up will be censored at their last known follow-up time.

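### Sections 15.5 and 15.9 tie censoring to participant contact although registry follow-up of the primary endpoint continues without it; the passages should be reconciled

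*Protocol*

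**What the plan says.** **Censoring.** Protocol section 15.5, on the efficacy endpoints of the full study: "participants who are lost to follow-up will be censored at their last known follow-up time". Section 15.9 adds, within the definition of the end of the study: "The date of the last point of contact will be the date of censor for participants who do not return a questionnaire".

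**Who counts as lost.** Section 9.6.1, under the heading for people temporarily not contactable, says of the week 4 and week 8 calls: "After three failed call attempts the participant is lost to follow up and the drug supply is stopped". For unreturned questionnaires it says: "After three failed call attempts the patient is lost to follow up and the drug supply is stopped". Yearly attempts to regain contact follow.

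**How primary events are found.** Besides questionnaires, section 11.3.1 states: "We will also use information from the Office for National Statistics, the Cancer Registry and Health Episode Statistics". Section 11.3.2 uses ONS, the cancer registry and "Health Episode Statistics to assess clinical primary and secondary outcomes". Section 13 says "HES data will also be accessed to provide evidence for potential endpoints", and this evidence goes into the packs that the events committee adjudicates. Agreement to HES access and ONS tagging is an inclusion criterion (9.1).

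**When follow-up ends.** Section 9.6: "Discontinuations from the study occur only if the participant explicitly withdraws consent for all forms of follow up". Section 9.6.2 lists participant questionnaires, GP questionnaires and registry follow-up as separate items that can be stopped one by one. Section 8.4 intends follow-up, where possible, for the full study period after study medication stops.

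No section says that registry coverage extends the censoring date of a participant who cannot be contacted, and none names a common registry cut-off date.

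**The concern.** The two halves of the plan use different clocks. Ascertainment of MI, stroke and CV death runs on registry coverage, which does not need the participant to answer. Censoring runs on contact. A participant who stops answering but has not withdrawn is still under observation for the primary endpoint, yet the text can be read as closing their follow-up.

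Two things are at stake. First, events that the trial can see would not count towards the 1,046. Second, the text leaves room for a mixed practice. Section 11.3.2 has registry events added to the database, while 15.9 sets the censoring date by contact. If both were followed, a non-responder with a registry event would be kept to the event date, and a non-responder without one would stop at last contact. Censoring would then depend on the outcome.

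**Working it through.** **Inputs.** From section 15.3: 2.2% annual event rate, 17% relative reduction (HR 0.83), 85% power, 16% lost to follow-up, 1,046 events, N = 12,898. From 15.1: two-sided 5%. From 9.3: 1:1 allocation. From 8.3: median follow-up about 5 years. Assumed here: constant hazards, 5 years for everyone, and last contact uniform over follow-up. Arm-specific non-response rates are also assumed, because the protocol gives only the overall 16%.

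**1. The plan's own figures.** Schoenfeld: 4 × (1.960 + 1.036)² / (ln 0.83)² = 1,035 events; Freedman gives 1,041. Power at 1,046 events is 85.4%. With annual compounding, 5-year risks are 10.5% and 8.8%, and N = 1,046 / mean risk / 0.84 = 12,885. With exponential risks N is 13,010. The stated 1,046 and 12,898 reproduce, so the sample size is not in error.

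**2. Events under complete registry follow-up.** Placebo risk: 1 − exp(−0.022 × 5) = 0.1042. Metformin risk: 1 − exp(−0.01826 × 5) = 0.0873. Mean 0.0957. Events: 12,898 × 0.0957 ≈ 1,234.

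**3. Events under literal contact censoring.** With last contact uniform on 0 to 5 years, the chance that the event comes before last contact is 1 − (1 − exp(−5λ)) / (5λ). This is 0.0530 (placebo) and 0.0443 (metformin), mean 0.0487. Events: 12,898 × (0.84 × 0.0957 + 0.16 × 0.0487) ≈ 1,137. Discarded: 1,234 − 1,137 ≈ 97, or 7.9%.

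**4. Cost in time.** If everyone started together, 1,046 events would be reached at about 4.2 years with complete registry follow-up and about 4.5 years under contact censoring. Both rules pass 1,046 within 5 years, so the planned power is kept.

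**5. Hazard ratio under the literal rule.** If censoring is unrelated to risk and later events are dropped, expected events equal λ × person-time in each arm, whatever the non-response rate. The ratio is 0.01826 / 0.022 = 0.83 even with 20% v 12% non-response.

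**6. Hazard ratio under the mixed practice.** All events count, but event-free non-responders (fraction d of an arm) lose on average 2.5 years each. Rate = p / (p/λ − 2.5 × d × exp(−5λ)), where p is the 5-year risk.

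| Non-response, metformin v placebo | Metformin rate | Placebo rate | Ratio |
|---|---|---|---|
| 16% v 16% | 0.08726 / (4.7785 − 0.3651) = 0.01977 | 0.10417 / (4.7348 − 0.3583) = 0.02380 | 0.83 |
| 18% v 14% | 0.08726 / (4.7785 − 0.4107) = 0.01998 | 0.10417 / (4.7348 − 0.3135) = 0.02356 | 0.85 |
| 20% v 12% | 0.08726 / (4.7785 − 0.4564) = 0.02019 | 0.10417 / (4.7348 − 0.2688) = 0.02332 | 0.87 |

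On the same formula a true ratio of 1.00 reads 1.02 and 1.04 in the last two rows.

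**7. Non-contact related to risk.** If the hazard doubles after non-response and rates are 20% v 12%, complete registry follow-up gives about 0.86, contact censoring about 0.83 and the mixed practice about 0.90. The choice of rule then changes the primary estimate.

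**The case against.** The case for leaving the text alone has several sound parts.

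- **The wording is not tied to the participant's questionnaire.** Section 15.9 speaks of the last point of contact and 15.5 of the last known follow-up time. Since 9.6.2 lists registry follow-up as a form of follow-up, 15.5 could include registry coverage. The 15.9 sentence may also govern only the final questionnaire. This stands as a possible reading, but the text does not settle it, and 9.6.1 defines loss by failed calls.
- **Section 9.6.1 is mainly a drug-supply rule** and describes a temporary status. That stands. The difficulty is that its label is the same one that triggers censoring in 15.5.
- **A reader might infer that the primary hazard ratio will be biased by arm-differential non-response.** The documents do not support this. Under the literal rule, differential non-response alone leaves it at 0.83. The shifts to 0.85 and 0.87 need a mixed practice that the protocol does not state and arm splits that are assumed.
- **A reader might infer that the 1,046 events shrink by about 80.** They do not. The 1,046 is a stopping target, and N already allows for 16% loss.
- **A reader might infer a breach of intention to treat.** Section 15.7 defines who is analysed and in which group, and a censored participant stays in that population.
- **HES supplies evidence, not confirmed events.** Adjudication may need medical records (13, 17.4), so not every registry-detectable event would be confirmed. That stands, and makes 97 an upper figure on these assumptions.
- **Censoring detail can sit in the statistical analysis plan,** which 15.6 promises. But 15.5 and 15.9 already state a rule, so the conflict is in the protocol itself.

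**Conclusion.** The point holds as an inconsistency that should be fixed, not as a demonstrated bias. The stated censoring rules, joined to the label in 9.6.1, can close a participant's follow-up while registries still observe them for the primary endpoint and 9.6 still counts them in the study. On the literal reading about 8% of registry-detectable events are discarded. In an event-driven trial that costs mainly time, some four months on the simple common-start assumption, and leaves the planned 85% power intact.

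Bias in the hazard ratio is possible in two circumstances only: non-contact related to risk, or registry events counted while event-free non-responders stop at last contact. The protocol gives no evidence on how non-response will differ by arm, so the illustrated values show the sensitivity and are not a forecast. All figures rest on constant hazards, 5 years of follow-up and uniform timing of last contact.

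**What to change.** In sections 15.5 and 15.9, separate the endpoints by how they are ascertained.

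- **Registry-ascertained endpoints:** censor event-free participants at one common cut-off date for which registry data are complete, whether or not questionnaires are returned. Censor earlier only at non-CV death, withdrawal from registry follow-up or loss of registry coverage. The cut-off must cover the Scottish source as well as ONS and HES, because 15.3 plans recruitment in Scotland and 18.1 names a separate Scottish data body.
- **Questionnaire-dependent outcomes:** keep the last point of contact.
- **Section 9.6.1:** rename the category 'not contactable', so that it no longer triggers the censoring rule in 15.5. The drug-supply rule in that section is not affected.

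The cost is a wording change, as the registry data are already planned. The small drawback is waiting until registry data are complete up to the cut-off before the analysis.

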#### 16 Data handling and record keeping

#### 16.1 Trial Master File

The Trial Master File (TMF) will be located at the MRC Epidemiology Unit, Cambridge Biomedical Campus in Cambridge and the other investigator sites will have Investigator Site Files (ISF). All essential documents to demonstrate the compliance of the study and study personnel with the conditions and principles of GCP and all applicable regulatory requirements will be stored in the Trial Master Files.

#### 16.2 Source Data

Study data will include data collected as part of the NHS Health Checks programme, data held in the existing research registries and data held in the databases of participating general practices. These source data will be entered into the eCRF by the research team at each site. For any data acquired that is entered directly into the eCRF, the eCRF will be considered as the source data. Consent forms and any outstanding tests required to confirm eligibility will be completed at the recruitment site. Data from annual questionnaires sent to participants and GPs will be entered into the eCRF by the study coordinators from GP and hospital records where necessary. These may include, but are not limited to, discharge summaries, ECGs, laboratory results, clinical charts, pharmacy records, and correspondence (collected from medical notes).

All documents will be stored safely in confidential conditions. Where possible, on study specific documents, the participant will be referred to by the study participant number, not by name. However, for some documents e.g. signed consent, participant and GP questionnaires, repeat prescription forms, the participant will be referred to by their name.

## 16.3 Data Protection & Patient Confidentiality

Local databases will be used to identify and recruit potential participants. Thereafter participants will be randomised and all study data will be entered into a Trial Management System Database using InferMed Macro software and validation procedures. Participants will be identified throughout by a study specific unique Participant ID number. A separate encrypted participant Contact Database will be used to store participant names, addresses, NHS numbers and other identifying details required for drug distribution. Access to the participant Contact Database will be restricted to the secure computer system used to facilitate distribution of the study medication, and Informatics personnel not otherwise involved in GLINT who can amend the details where changes are required.

Local sites will store source data for each participant. This will be labelled with the participant's study number, initials and date of birth. Data will include the original signed and dated consent form, the results of any laboratory tests or procedures carried out and any additional documentation obtained to support events reported in the annual questionnaires.

The eCRF will also be considered source data for any data obtained from the participant during the baseline visits that is immediately entered onto the eCRF. Table 2 lists what data and the source from where it is to be obtained.

Data	Source
Consent	Consent form
Medical screening	eCRF
Socio-demographic	eCRF
Height	eCRF
Weight	eCRF
BMI	eCRF
BP	eCRF
Qualifying labs	Source database

Lab results	Biochemistry output (varying at different sites)
Drug accountability	eCRF/questionnaire (depending on time point in study)
Drug satisfaction	Participant Questionnaire
Participant reported CV events	Participant Questionnaire
Participant reported cancer events	Participant Questionnaire
Participant reported diabetes	Participant Questionnaire
EQ5D	Participant Questionnaire
SF8	Participant Questionnaire
HERC	Participant Questionnaire
GP reported events	GP Questionnaire
Pregnancy	GP Questionnaire
Medication list	eCRF
AE/SAE form	eCRF or paper CRF

#### Table 2: Source of data

Source documents for other data points will be kept in local coordinating centres and entered onto the eCRF by the study coordinator. The DTU will send out the annual questionnaires to the participants and their GPs and enter the data on receipt of the completed documents.

GLINT staff will ensure that the participants' anonymity is maintained. The participants will be identified only by initials and a participant ID number on the CRF and Trial Management System Database. Consent forms, GP questionnaires and participant questionnaires will contain participant names. All documents will be stored securely and only accessible by study staff and authorised personnel. The study will comply with the Data Protection Act which requires data to be anonymised as soon as it is practical to do so.

All investigators and study site staff involved in this study must comply with the requirements of the Data Protection Act 1998 and Trust Policy with regards to the collection, storage, processing and disclosure of personal information and will uphold the Act's core principles.

# **17 Study Committees**

#### 17.1 Trial Steering Committee

The GLINT Trial Steering Committee (TSC) will have responsibility for the oversight of the study (Figure 1). The TSC will consist of nine individuals, comprising three senior independent academic representatives who are experts in their field (one of whom will chair the committee), four GLINT PIs, one lay representative and a Sponsor representative. A TSC charter will delineate operating procedures. The TSC is the main decision-making body for GLINT and is charged with the overall scientific, professional, and operational conduct of the study. The primary functions of the TSC are to:

1. Review and approve the study protocol and all protocol amendments.

2. Supervise the conduct of the study in accordance with its responsibilities described in the study protocol.

- 3. Review and approve the Statistical Analysis Plan.
- 4. Oversee all study subcommittees, including but not limited to:
  - Clinical endpoint committee
  - Data monitoring and ethics committee

• Operational committee

5. Review and consider recommendations from the IDMC

6. The TSC will determine the time to terminate the study, based on recommendations from the IDMC and other available information. The TSC may also find it necessary to terminate the study under certain circumstances, including but not limited to the following reasons:

• Animal, human or toxicological test results, in the reasonable determination of the TSC, support termination of the study

• Ethical or participant safety issues occur that the TSC feels support termination of the study

• Extraordinary scientific, regulatory or other events that negatively impact the rationale for the study such that the TSC agrees it is appropriate to terminate the study 7. Review all sub-study requests and approve where appropriate.

8. Consider, authorise as appropriate and prioritise requests for access to GLINT study data and genetic samples for academic or other collaborations. After the TSC disbands, the MRC Epidemiology Unit, DTU and the sponsor will assume this responsibility.

9. Approve the communication strategy on how to best communicate information about the progress of the study.

10. Ensure accurate, uniform, timely, and high quality reporting of the full study and all approved sub-studies.

11. All members of the TSC will have access, in confidence to the draft manuscript describing the primary results paper.

